12. MEASUREMENT OF EFFECT

12.1 Antitumor Effect – Solid Tumors

For the purposes of this study, patients will be re-evaluated for response every 6 weeks. In addition to a baseline scan, confirmatory scans should also be obtained 4 weeks following initial documentation of objective response.

Response and progression will be evaluated in this study using the new international criteria proposed by the revised Response Evaluation Criteria in Solid Tumors (RECIST) guideline (version 1.1). Changes in the largest diameter (unidimensional measurement) of the tumor lesions and the shortest diameter in the case of malignant lymph nodes are used in the RECIST criteria.

12.1.1 Definitions

Evaluable for toxicity: All patients will be evaluable for toxicity from the time of their first treatment with MGCD516.

Evaluable for objective response: Only those patients who have measurable disease present at baseline, have received at least one cycle of therapy, and have had their disease re-evaluated will be considered evaluable for response. These patients will have their response classified according to the definitions stated below. (Note: Patients who exhibit objective disease progression prior to the end of cycle 1 will also be considered evaluable.)

Evaluable Non-Target Disease Response: Patients who have lesions present at baseline that are evaluable but do not meet the definitions of measurable disease, have received at least one cycle of therapy, and have had their disease re-evaluated will be considered evaluable for non-target disease. The response assessment is based on the presence, absence, or unequivocal progression of the lesions.

12.2 Disease Parameters

Measurable disease: Measurable lesions are defined as those that can be accurately measured in at least one dimension (longest diameter to be recorded for non-nodal lesions and short axis for nodal lesions) as \geq 20 mm by chest x-ray, as \geq 10 mm with CT scan, or \geq 10 mm with calipers by

clinical exam. All tumor measurements must be recorded in millimeters (or decimal fractions of centimeters).

Note: Tumor lesions that are situated in a previously irradiated area might or might not be considered measurable. If the investigator thinks it appropriate to include them, the conditions under which such lesions should be considered must be defined in the protocol.

Malignant lymph nodes: To be considered pathologically enlarged and measurable, a lymph node must be ≥15 mm in short axis when assessed by CT scan (CT scan slice thickness recommended to be no greater than 5 mm). At baseline and in follow-up, only the short axis will be measured and followed.

Non-measurable disease: All other lesions (or sites of disease), including small lesions (longest diameter <10 mm or pathological lymph nodes with ≥ 10 to <15 mm short axis), are considered non-measurable disease. Bone lesions, leptomeningeal disease, ascites, pleural/pericardial effusions, lymphangitis cutis/pulmonitis, inflammatory breast disease, and abdominal masses (not followed by CT or MRI), are considered as non-measurable.

Note: Cystic lesions that meet the criteria for radiographically defined simple cysts should not be considered as malignant lesions (neither measurable nor non-measurable) since they are, by definition, simple cysts. Cystic lesions thought to represent cystic metastases can be considered as measurable lesions, if they meet the definition of measurability described above. However, if non-cystic lesions are present in the same patient, these are preferred for selection as target lesions.

Target lesions: All measurable lesions up to a maximum of 2 lesions per organ and 5 lesions in total, representative of all involved organs, should be identified as target lesions and recorded and measured at baseline. Target lesions should be selected on the basis of their size (lesions with the longest diameter), be representative of all involved organs, but in addition should be those that lend themselves to reproducible repeated measurements. It may be the case that, on occasion, the largest lesion does not lend itself to reproducible measurement in which circumstance the next largest lesion which can be measured reproducibly should be selected. A sum of the diameters (longest for non-nodal lesions, short axis for nodal lesions) for all target lesions will be calculated and reported as the baseline sum diameters. If lymph nodes are to be included in the sum, then only the short axis is added into the sum. The baseline sum diameters will be used as reference to further characterize any objective tumor regression in the measurable dimension of the disease.

Non-target lesions: All other lesions (or sites of disease) including any measurable lesions over and above the 5 target lesions should be identified as non-target lesions and should also be recorded at baseline. Measurements of these lesions are not required, but the presence, absence, or in rare cases unequivocal progression of each should be noted throughout follow-up.

12.3 Methods for Evaluation of Measurable Disease

All measurements should be taken and recorded in metric notation using a ruler or calipers. All

baseline evaluations should be performed as closely as possible to the beginning of treatment and never more than 4 weeks before the beginning of the treatment.

The same method of assessment and the same technique should be used to characterize each identified and reported lesion at baseline and during follow-up. Imaging-based evaluation is preferred to evaluation by clinical examination unless the lesion(s) being followed cannot be imaged but are assessable by clinical exam.

Clinical lesions: Clinical lesions will only be considered measurable when they are superficial (e.g., skin nodules and palpable lymph nodes) and ≥10 mm diameter as assessed using calipers (e.g., skin nodules). In the case of skin lesions, documentation by color photography, including a ruler to estimate the size of the lesion, is recommended.

Chest x-ray: Lesions on chest x-ray are acceptable as measurable lesions when they are clearly defined and surrounded by aerated lung. However, CT is preferable.

Conventional CT and MRI: This guideline has defined measurability of lesions on CT scan based on the assumption that CT slice thickness is 5 mm or less. If CT scans have slice thickness greater than 5 mm, the minimum size for a measurable lesion should be twice the slice thickness. MRI is also acceptable in certain situations (e.g., for body scans).

Use of MRI remains a complex issue. MRI has excellent contrast, spatial, and temporal resolution; however, there are many image acquisition variables involved in MRI, which greatly impact image quality, lesion conspicuity, and measurement. Furthermore, the availability of MRI is variable globally. As with CT, if an MRI is performed, the technical specifications of the scanning sequences used should be optimized for the evaluation of the type and site of disease. Furthermore, as with CT, the modality used at follow-up should be the same as was used at baseline and the lesions should be measured/assessed on the same pulse sequence. It is beyond the scope of the RECIST guidelines to prescribe specific MRI pulse sequence parameters for all scanners, body parts, and diseases. Ideally, the same type of scanner should be used and the image acquisition protocol should be followed as closely as possible to prior scans. Body scans should be performed with breath-hold scanning techniques, if possible.

PET-CT: At present, the low dose or attenuation correction CT portion of a combined PET-CT is not always of optimal diagnostic CT quality for use with RECIST measurements. However, if the site can document that the CT performed as part of a PET-CT is of identical diagnostic quality to a diagnostic CT (with IV and oral contrast), then the CT portion of the PET-CT can be used for RECIST measurements and can be used interchangeably with conventional CT in accurately measuring cancer lesions over time. Note, however, that the PET portion of the CT introduces additional data which may bias an investigator if it is not routinely or serially performed.

Ultrasound: Ultrasound is not useful in assessment of lesion size and should not be used as a method of measurement. Ultrasound examinations cannot be reproduced in their entirety for independent review at a later date and, because they are operator dependent, it cannot be guaranteed that the same technique and measurements will be taken from one assessment to the

next. If new lesions are identified by ultrasound in the course of the study, confirmation by CT or MRI is advised. If there is concern about radiation exposure at CT, MRI may be used instead of CT in selected instances.

Endoscopy/Laparoscopy: The utilization of these techniques for objective tumor evaluation is not advised. However, such techniques may be useful to confirm complete pathological response when biopsies are obtained or to determine relapse in trials where recurrence following complete response (CR) or surgical resection is an endpoint.

Tumor markers: Tumor markers will not be used in this study.

Cytology/Histology: These techniques can be used to differentiate between partial responses (PR) and complete responses (CR) in rare cases (e.g., residual lesions in tumor types, such as germ cell tumors, where known residual benign tumors can remain).

The cytological confirmation of the neoplastic origin of any effusion that appears or worsens during treatment when the measurable tumor has met criteria for response or stable disease is mandatory to differentiate between response or stable disease (an effusion may be a side effect of the treatment) and progressive disease.

FDG-PET: While FDG-PET response assessments need additional study, it is sometimes reasonable to incorporate the use of FDG-PET scanning to complement CT scanning in assessment of progression (particularly possible 'new' disease). New lesions on the basis of FDG-PET imaging can be identified according to the following algorithm:

- Negative FDG-PET at baseline, with a positive FDG-PET at follow-up is a sign of PD based on a new lesion.
- No FDG-PET at baseline and a positive FDG-PET at follow-up: If the positive FDG-PET at follow-up corresponds to a new site of disease confirmed by CT, this is PD. If the positive FDG-PET at follow-up is not confirmed as a new site of disease on CT, additional follow-up CT scans are needed to determine if there is truly progression occurring at that site (if so, the date of PD will be the date of the initial abnormal FDG-PET scan). If the positive FDG-PET at follow-up corresponds to a pre-existing site of disease on CT that is not progressing on the basis of the anatomic images, this is not PD.
- FDG-PET may be used to upgrade a response to a CR in a manner similar to a biopsy in cases where a residual radiographic abnormality is thought to represent fibrosis or scarring. The use of FDG-PET in this circumstance should be prospectively described in the protocol and supported by disease-specific medical literature for the indication. However, it must be acknowledged that both approaches may lead to false positive CR due to limitations of FDG-PET and biopsy resolution/sensitivity.

Note: A 'positive' FDG-PET scan lesion means one which is FDG avid with an uptake greater

than twice that of the surrounding tissue on the attenuation corrected image.

12.4 Response Criteria

12.4.1 Evaluation of Target Lesions

Complete Response (CR): Disappearance of all target lesions. Any pathological lymph nodes (whether target or non-target) must have reduction in short axis to <10 mm.

Partial Response (PR): At least a 30% decrease in the sum of the diameters of target lesions, taking as reference the baseline sum diameters.

Progressive Disease (PD): At least a 20% increase in the sum of the diameters of target lesions, taking as reference the smallest sum on study (this includes the baseline sum if that is the smallest on study). In addition to the relative increase of 20%, the sum must also demonstrate an absolute increase of at least 5 mm. (Note: the appearance of one or more new lesions is also considered progressions).

Stable Disease (SD): Neither sufficient shrinkage to qualify for PR nor sufficient increase to qualify for PD, taking as reference the smallest sum diameters while on study.

12.4.2 Evaluation of Non-Target Lesions

Complete Response (CR): Disappearance of all non-target lesions and normalization of tumor marker level. All lymph nodes must be non-pathological in size (<10 mm short axis).

Note: If tumor markers are initially above the upper normal limit, they must normalize for a patient to be considered in complete clinical response.

Non-CR/Non-PD: Persistence of one or more non-target lesion(s) and/or maintenance of tumor marker level above the normal limits.

Progressive Disease (PD): Appearance of one or more new lesions and/or unequivocal progression of existing non-target lesions. Unequivocal progression should not normally trump target lesion status. It must be representative of overall disease status change, not a single lesion increase. Although a clear progression of "non-target" lesions only is exceptional, the opinion of the treating physician should prevail in such circumstances, and the progression status should be confirmed at a later time by the review panel (or Principal Investigator).

12.4.3 Evaluation of Best Overall Response

The best overall response is the best response recorded from the start of the treatment until disease progression/recurrence (taking as reference for progressive disease the smallest measurements recorded since the treatment started). The patient's best response assignment will depend on the achievement of both measurement and confirmation criteria.

Target Lesions	Non-Target Lesions	New Lesions	Overall Response	Best Overall Response when Confirmation is Required*
CR	CR	No	CR	≥4 wks.
				Confirmation**
CR	Non-CR/Non-PD	No	PR	
CR	Not evaluated	No	PR	≥4 wks.
PR	Non-CR/Non-PD/not	No	PR	Confirmation**
	evaluated			
SD	Non-CR/Non-PD/not	No	SD	documented at least
	evaluated			once ≥4 wks. from
				baseline**
PD	Any	Yes or	PD	
		No		
Any	PD***	Yes or	PD	no prior SD, PR or CR
		No		
Any	Any	Yes	PD	

^{*} See RECIST 1.1 manuscript for further details on what is evidence of a new lesion.

Note: Patients with a global deterioration of health status requiring discontinuation of treatment without objective evidence of disease progression at that time should be reported as "symptomatic deterioration." Every effort should be made to document the objective progression even after discontinuation of treatment.

12.5 **Duration of Response**

Duration of overall response: The duration of overall response is measured from the time measurement criteria are met for CR or PR (whichever is first recorded) until the first date that recurrent or progressive disease is objectively documented (taking as reference for progressive disease the smallest measurements recorded since the treatment started).

The duration of overall CR is measured from the time measurement criteria are first met for CR until the first date that progressive disease is objectively documented.

Duration of stable disease: Stable disease is measured from the start of the treatment until the criteria for progression are met, taking as reference the smallest measurements recorded since the treatment started, including the baseline measurements.

^{**} Only for non-randomized trials with response as primary endpoint.

^{***} In exceptional circumstances, unequivocal progression in non-target lesions may be accepted as disease progression.

12.6 Progression-Free Survival

Progression free survival is defined as the duration of time from start of treatment to time of progression or death, whichever occurs first.

12.7 Response Review

Not applicable.

12.8 Unblinding Procedures

Not applicable.

12.9 Stopping Rules

Adverse event stopping rule: Accrual will be temporarily suspended to this study if (a) at any time, 2 patients have experienced a grade 5 event considered at least possibly related to the study treatment and not related to disease progression or (b) more than 40% of all patients, when accrual is equal to or greater than 10 patients, have experienced a grade 3 or higher adverse event. In addition, each grade 5 event will be reviewed at the time of occurrence to determine whether study accrual should be suspended to protect the safety of patients. This adverse event stopping rule may be altered in the event of the study reopening after a temporary suspension or should new information become available related to the safety of the study drug.

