- unexpected (in terms of nature, severity or frequency) given (a) the research procedures that are described in the IRB-approval protocol and informed consent document, and (b) the characteristics of the subject population being studied:
- related or possibly related to participation in such research (e.g., there is a reasonable possibility that the incident, experience or outcome may have been caused by the procedures involved in such research); and

 suggests that the research places subjects or others at a greater risk of harm (including physical, psychological, economic or social harm) than was previously known or recognized.

Adverse Event Reporting Period: The study period during which adverse events must be reported is normally defined as the period from the initiation of any study procedures (after the first dose of study treatment) to the end of the study treatment (last dose of study treatment) and follow-up. For this study, the study treatment follow-up period is defined as 28 days following the last administration of study treatment.

Baseline/Preexisting Condition: A baseline/preexisting condition is one that is present at the start of the study. A preexisting condition should be recorded as an adverse event if the frequency, intensity, or if the character of the condition worsens during the study period.

General Physical Examination Findings: At screening, any clinically significant abnormality should be recorded as a preexisting condition. At the end of the study, any new clinically significant findings/abnormalities that meet the definition of an adverse event must also be recorded and documented as an adverse event.

Post-study Adverse Event: All unresolved adverse events should be followed by the investigator until the events are resolved, the subject is lost to follow-up, or the adverse event is otherwise explained. At the last scheduled visit, the investigator should instruct each subject to report any subsequent event(s) that the subject, or the subject's personal physician, believes might reasonably be related to participation in this study.

Abnormal Laboratory Values: A clinical laboratory abnormality should be documented as an adverse event if any one of the following conditions is met:

- The laboratory abnormality is not otherwise refuted by a repeat test to confirm the abnormality
- The abnormality suggests a disease and/or organ toxicity

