14.3 Data and Safety Monitoring Committee

The NCI-approved Data Safety and Monitoring Committee (DSMC) of the Herbert Irving Comprehensive Cancer Center (HICCC) will monitor every subject who receives treatment on this protocol for toxicity. This protocol will adhere to the policies of the currently approved HICCC Data and Safety Monitoring Plan (DSMP), which is in accordance with NCI and CUMC-IRB policy and guidelines. The committee is chair is appointed by the HICCC Director. The committee consists of HICCC faculty and staff with expertise in oncology, research pharmacy, research nursing, and data management. The DSMC convenes twice a month to review patient safety and the conduct of the trial. The PI will submit data and safety monitoring reports to the DSMC at a frequency to be determined by the DSMC based on risk to the subjects.

At the time of renewal, the study team will submit the most recent DSMC approval letter for safety review to the CUMC IRB. Any modifications that are required by the DSMC to ensure patient safety will be submitted to the IRB. All protocol deviations, violations, and eligibility waivers will be submitted to and approved by the DSMC prior to being reported to the IRB. All study data reviewed and discussed during these meetings will be kept confidential.

For multicenter research, the principal investigator will assure that there is a mechanism in place to distribute the report to all participating investigators for submission to their local IRB. The report will document that a review of data and outcomes across all centers took place on a given date. It will summarize the DSMC's review of the cumulative toxicities reported from all participating sites without specific disclosure by treatment arm. It will also inform site investigators of the study the DSMC's conclusion with respect to progress or need for modification of the protocol.

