15.2 Size/Accrual Rate

The sample size is 29 patients. We may enroll up to an additional 2 patients to account for patients declared non-evaluable and patients failing to initiate the first cycle of treatment. The planned accrual rate across both sites is 2-3 patients per month. Therefore, accrual is expected to be complete in approximately 10 to 15 months. Assuming patients are permitted to continue treatment for up to 1 year (12 months) and allowing 6 months for quality assurance, the anticipated duration of the study is approximately 28 to 33 months.

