15.6 Reporting and Exclusions

15.6.1 Evaluation of toxicity

The safety population will consist of all patients who received at least one dose of study drug.

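### Does the 40% toxicity rule for suspending accrual need its denominator and look times spelled out?

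*Combined protocol and SAP*

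**What the plan says.** Section 12.9 has two conditions for temporarily suspending accrual. Limb (a) applies if "at any time, 2 patients have experienced a grade 5 event" that is at least possibly related to treatment and not due to progression. Limb (b) applies if "more than 40% of all patients, when accrual is equal to or greater than 10 patients, have experienced a grade 3 or higher adverse event". Each grade 5 event is also reviewed when it occurs, and the rule may be altered after a suspension or on new safety information.

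Other sections bear on who is counted:
- Section 9.2 runs adverse event reporting "from the initiation of any study procedures (after the first dose of study treatment") to 28 days after the last dose.
- Section 12.1.1: "All patients will be evaluable for toxicity from the time of their first treatment with MGCD516".
- Section 15.6.1: "The safety population will consist of all patients who received at least one dose of study drug".
- Section 14.3 gives the Data and Safety Monitoring Committee (DSMC) the task of monitoring toxicity in the subjects who receive treatment.
- Section 15.2 allows up to 2 extra patients for "patients declared non-evaluable and patients failing to initiate the first cycle of treatment".

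On timing, Section 14.3 has the DSMC meeting twice a month and adds: "The PI will submit data and safety monitoring reports to the DSMC at a frequency to be determined by the DSMC". Section 14.4 has the Compliance Coordinator summarise stopping rules for the full DSMC at its regular meetings. Section 15.2 states: "The planned accrual rate across both sites is 2-3 patients per month".

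**The concern.** Limb (b) uses accrual as its yardstick, and accrual normally means registration. Registration precedes treatment (Section 6.1), and Section 15.2 foresees patients who never start. If registered patients form the denominator, someone never dosed adds to it but would hardly ever add to the numerator, and someone registered days ago counts as event-free. No minimum time on drug is required. The words that make limb (a) continuous are not repeated in limb (b), the frequency of the investigator's reports is left to the DSMC, and no probability of firing is stated.

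Two people could therefore apply the rule to the same events and disagree, with the registered reading leaning toward a later pause or none. Limb (b) is the only numerical trigger for non-fatal toxicity, so this deserved a check.

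**Working it through.** **Inputs.** Threshold strictly above 40%, from 10 patients (12.9); sample size 29, up to 2 extra, accrual 2-3 per month (15.2); DSMC meetings twice a month (14.3). The plan states no firing probability, so there is no figure to reproduce. The true rate of patients with a grade 3 or higher event is not given; 30%, 40%, 50% and 60% are assumed.

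**1. Boundary.** The rule fires at the smallest whole number k with k/n > 0.40, that is k = floor(0.4n) + 1.

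| Patients n | 10-12 | 13-14 | 15-17 | 18-19 | 20-22 | 23-24 | 25-27 | 28-29 | 30-31 |
|---|---|---|---|---|---|---|---|---|---|
| Events needed | 5 | 6 | 7 | 8 | 9 | 10 | 11 | 12 | 13 |

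**2. Effect of the denominator with events fixed.** 5/12 = 41.7% fires and 5/13 = 38.5% does not. 12/29 = 41.4% fires; 12/30 = 40.0% and 12/31 = 38.7% do not. Comparing the boundary at n with that at n + 1, one undosed patient raises the count needed by one at 8 of the 20 sizes from 10 to 29 (12, 14, 17, 19, 22, 24, 27, 29). Two undosed patients raise it at 16 of 20, all except multiples of 5. The rise is one event in every case.

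**3. Chance of ever firing.** Start with no events. For each further patient whose status is known, update P(k events) = P(k) × (1 − p) + P(k − 1) × p. At each look, move the probability at or above the boundary to fired.

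| Reading | p = 30% | 40% | 50% | 60% |
|---|---|---|---|---|
| Dosed patients, look at every n from 10 to 29 | 0.373 | 0.737 | 0.945 | 0.995 |
| Dosed patients, look at every second n (10, 12, ..., 28) | 0.354 | 0.711 | 0.932 | 0.993 |
| One undosed patient always counted, every accrual 10-29 | 0.306 | 0.671 | 0.918 | 0.991 |
| Two undosed patients always counted, every accrual 10-29 | 0.242 | 0.595 | 0.881 | 0.985 |

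**4. Look times.** Twice-monthly meetings give one look per 2/2 = 1 to 3/2 = 1.5 patients. The every-second-patient row is therefore sparser than the meeting calendar, yet it loses only 0.373 − 0.354 = 0.019, 0.737 − 0.711 = 0.026, 0.945 − 0.932 = 0.013 and 0.995 − 0.993 = 0.002. Much sparser schedules, such as one look at 10 patients, would lose more. But the wording covers 10 or more patients, which makes limb (b) a standing condition, and no section supports a single look.

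**5. Denominator.** Two undosed patients counted throughout lower the chance by 0.373 − 0.242 = 0.131 at 30%, 0.737 − 0.595 = 0.142 at 40%, 0.945 − 0.881 = 0.064 at 50% and 0.995 − 0.985 = 0.010 at 60%. One lowers it by 0.067, 0.066, 0.027 and 0.004. The two-patient case is the extreme: it needs the whole Section 15.2 allowance to be never-dosed patients, all present by the tenth accrual, although that allowance also covers non-evaluable patients, who may have been dosed.

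**The case for a change.** The strongest case for a change is that limb (b) cannot be applied in one way from Section 12.9 alone. That section never refers to the safety population, and its own yardstick points the other way. One undosed patient is enough to change the answer at 8 of 20 sizes, and Section 15.2 expects such patients. A clarification would take a few sentences and no new data, since first-treatment dates are already needed for survival times (15.4) and event timing is recorded (9.3).

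The part about the denominator stands as a fact: a cross-reference is missing. Its weight is small. Each section that defines who is at risk of toxicity uses treated patients, and no section defines a registered-patient safety set. The text on undosed patients is also less clear-cut than it seems, because the study calendar in Section 11 marks adverse event assessment at screening, so it is an inference that such patients can never enter the numerator.

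The part about look times does not stand, for the reasons in step 4 of the working. The report frequency left open in Section 14.3 concerns the investigator's reports; the stopping-rule summaries under Section 14.4 are a separate route.

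A minimum time on drug and published firing probabilities would be useful additions, but nothing in the plan promises them. With a standing check, a recent patient's event is counted when it occurs, so the lack of a minimum mainly delays a pause.

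**Conclusion.** No change to the plan is called for. This is a gap in detail that the DSMC and the trial statistician would fill sensibly from Sections 12.1.1, 14.3 and 15.6.1 and the committee's own meetings.

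The two readings differ by one event at most, and only when the count lies at the edge of the limit. In the extreme case of two undosed patients counted throughout, the chance of firing falls by up to 0.142 (at an assumed 40% rate); at 60%, where a pause matters more, the fall is 0.010. Uncertainty over look times costs at most 0.026. The result of the rule is a temporary pause in accrual. Limb (a), the review of every grade 5 event and DSMC toxicity review apply whichever way limb (b) is read, and the Simon decision does not depend on it.

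These probabilities rest on assumed event rates, independent patients and event status known for each dosed patient at each look. The boundary and the same-events comparisons rest on the protocol's wording alone. No view is taken on whether 40% is the right limit.
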